6.2 PATIENT DISPOSITION

The number and percentage of subjects in each of the following groups will be presented in a by-subject listing and summarized by disease and cohort:

- Subjects screened
- Subjects screen failed
- Subjects enrolled

- Subjects included in each analysis set
- Subjects who have completed treatment (defined as receiving four doses)
- Subjects who have completed study (defined as completing the follow-up visit)
- Subjects who have discontinued from the study including the reasons for discontinuation

Enrolled subjects are those who are not a screen failure.

6.3 DEMOGRAPHIC AND BASELINE CHARACTERISTICS

6.3.1 Demographic and Baseline Characteristics

Demographic variables will include age, sex, race, and ethnicity. Baseline characteristics include height (cm), weight (kg), body mass index (BMI; kg/m2), and time since diagnosis (</=10 years vs >10 years). Demographics and baseline characteristics will be presented in a by-subject listing and summarized by disease and cohort using the safety analysis set.

6.3.2 Baseline Disease Status/Disease History

Crohn's Disease and Ulcerative Colitis history will be presented in by-subject listings using the safety analysis set.

6.3.3 Medical History

Medical history conditions will be collected at screening. The number of subjects with any medical history will be presented in a by-subject listing using the safety analysis set.

6.3.4 Prior and Concomitant Medications

Prior medications are those received prior to the start of the study drug administration. Any medication that stops on or after the start of the first study drug administration or with missing stop dates is considered a concomitant medication. A medication can be both prior and concomitant (e.g., a medication that started before first dose and is ongoing at the end of the study).

Prior and concomitant medications will be coded using World Health Organization Drug Dictionary Anatomical Therapeutic Chemical (WHO/ATC) classification index version 2020-03-01, ATC Level 3. The number and percentage of subjects who take prior and concomitant medications will be summarized by drug class and preferred term, disease and cohort for the safety analysis set.

All medications captured in CRFs will also be presented in a by-subject listing.

6.4 PROTOCOL DEVIATIONS

Protocol deviations will be collected in a tracker and presented in a by-subject listing including description, category/type, and importance (Important or Not Important) as determined by Avalo prior to database lock. Important deviations will be summarized by disease and cohort by category/type for the safety analysis set.

7. MEASUREMENTS OF TREATMENT EXPOSURE AND COMPLIANCE

Because study medication is administered at the study center by trained study personnel, compliance with respect to study medication will not be calculated. The total number of doses/injections and number of days exposed to study drug (defined in Section 5.3) will be summarized by disease and cohort for the safety analysis set. A listing of study drug administration and exposure data will be provided.

8. EFFICACY EVALUATION

8.1 EFFICACY ENDPOINT(S)

8.1.1 Primary Efficacy Endpoints

CD subjects only:

• Change from baseline in SES-CD total score at Visit 10 (Day 56/ET)

UC subjects only:

• Change from baseline in Modified Endoscopic Score at Visit 10 (Day 56/ET)

8.1.2 Secondary Efficacy Endpoint(s)

CD subjects only:

- Change from baseline in CDAI item and total scores at Visits 4 (Day 14), 6 (Day 28), and 8 (Day 42)
- Change from baseline in number of total stools for 7-day interval averages from Visit 3 (Day 7) to Visit 10 (Day 56/ET)
- Change from baseline in number of loose/watery stools for 7-day interval averages from Visit 3 (Day 7) to Visit 10 (Day 56/ET)
- Change from baseline in abdominal pain score for 7-day interval averages from Visit 3 (Day 7) to Visit 10 (Day 56/ET)
- Change from baseline in general well-being for 7-day interval averages from Visit 3 (Day 7) to Visit 10 (Day 56/ET)

UC subjects only:

- Change from baseline in stool frequency for 7-day interval averages from Visit 3 (Day 7) to Visit 10 (Day 56/ET)
- Change from baseline in rectal bleeding for 7-day interval averages from Visit 3 (Day 7) to Visit 10 (Day 56/ET)

• Change from baseline in Modified Mayo Score at Visit 10 (Day 56/ET)

Both CD and UC subjects:

• Change from baseline in IBD-Q total score at Visit 10 (Day 56/ET)

8.2 EFFICACY ANALYSIS

The efficacy analyses will be conducted using the full analysis set as defined in Section 6.1, unless otherwise stated.

The efficacy endpoints mentioned in section 8.1 are described in detail in section 4.

No statistical tests will be generated. Only descriptive statistics will be presented.

8.2.1 Primary Efficacy Analyses

SES-CD (CD subjects only)

The SES-CD total score and the variable scores will be summarized by cohort and visit using continuous and categorical disease severity summaries; the change from baseline for each post-baseline visit will also be summarized.

SES-CD total score and the variable scores will be presented in a listing.

Modified Endoscopic Score (UC subjects only)

Mean Modified Endoscopic Score will be summarized for baseline and Visit 10 (Day 56/ET) using continuous summaries; the change from baseline will also be summarized.

Modified Endoscopic Score will be presented in a listing.

8.2.2 Supportive and Sensitivity Analyses of the Primary Endpoint

Not applicable.

8.2.3 Secondary Efficacy Analyses

CD subjects only:

CDAI

The CDAI item and total scores will be summarized by cohort and visit using continuous summaries; the change from baseline for each post-baseline visit will also be summarized.

Disease severity as defined by the CDAI total score will be summarized by cohort and visit using categorical summaries: Remission (<150); Mild (150 - 219); Moderate (220 - 450); Severe (> 450).

The CDAI total score and each of the 8 item scores will be presented in a listing. Listings will also be provided for daily diary data, as well as non-diary item data and CDAI related questions.

Abdominal Pain, Frequency of Loose Stools, and Total Stools

Mean abdominal pain score, frequency of loose stools, total stools, and general well-being will be summarized for baseline and post-baseline visits by cohort and 7-day interval averages (corresponding to weekly visit dates) using continuous summaries; the change from baseline for each post-baseline visit will also be summarized.

Since these endpoints are collected in the CD subject diary, they will be presented together in one listing.

UC subjects only:

Stool Frequency and Rectal Bleeding

Mean stool frequency and rectal bleeding will be summarized for baseline and post-baseline visits by 7-day interval averages (corresponding to weekly visit dates) using continuous summaries; the change from baseline for each post-baseline visit will also be summarized.

Since these endpoints are collected in the UC subject diary, they will be presented together in one listing.

Modified Mayo Score

The Modified Mayo Score will be summarized by visit using continuous summaries; the change from baseline for each post-baseline visit will also be summarized.

The Modified Mayo Score and each of the 3 criteria will be presented in a listing.

Both CD and UC subjects:

IBD-Q

The IBD-Q total score and the domain scores (Bowel; Systemic; Emotional; and Social) will be summarized by disease, cohort, and visit using continuous summaries; the change from baseline to Visit 10/ET will also be summarized.

IBD-Q data will be presented in a listing.

9. SAFETY EVALUATIONS

9.1 OVERVIEW OF SAFETY ANALYSIS METHODS

The safety analyses will be conducted using the safety analysis set as defined in Section 6.1, unless otherwise stated.

9.2 ADVERSE EVENTS

Any untoward medical event that occurs after signing the informed consent form (ICF) is considered to be an adverse event (AE). Adverse events recorded between the time of signature of informed consent until the first dose administration will be considered baseline signs and/or symptoms.

A treatment-emergent adverse event (TEAE) is an adverse event with onset on or after the first dose administration date or an adverse event present before the first dose administration date that worsens (i.e., increases in severity) on or after the first dose administration date. TEAEs will be summarized from the first dose administration date through:

- the Safety Follow-Up/Visit 11 for subjects who completed the study or
- 28 days after the last dose administration date for subjects who discontinued prematurely from the study.

Verbatim terms used by investigators to identify AEs in the CRFs will be coded to the appropriate preferred term (PT) and system organ class (SOC) using a standardized coding dictionary (MedDRA Version 23.0 April 2020). All coding will be reviewed prior to database lock. All recorded AEs will be listed, but only TEAEs will be summarized.

Adverse events will be classified according to severity (CTCAE Grades 1-5) and relationship to study drug (not related, possibly related, or probably related). For summary tables, a "related" adverse event is one judged to be possibly related or probably related to study drug.

The following adverse event categories will be summarized by disease and cohort:

- Overall TEAEs
- TEAEs related to study drug
- TEAEs leading to discontinuation
- Serious AEs
- Severe TEAEs (Grade 3 or higher)

The number of subjects with AEs will be further summarized by SOC and PT (TEAEs, as well as related TEAEs), by PT only, and by SOC, PT and severity. Sorting will be in descending order of frequency.

If a patient has multiple occurrences of a TEAE within the same SOC and PT, only the most related or most severe will be included in the summaries.

Separate listings for all AEs, serious AEs, and AEs leading to discontinuation will be generated.

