12.3.1.6.2. Definition of Adverse Events, Period of Observation and Recording of Adverse Events

An AE is defined as any untoward medical occurrence in a clinical investigation subject administered a pharmaceutical product that does not necessarily have a causal relationship with the product. An AE can therefore be any unfavorable and unintended sign (including a new, clinically important abnormal laboratory finding), symptom, or disease, temporally associated with the product, whether or not related to the product.

All AEs are collected from the time of the informed consent is signed until the final safety follow-up visit (described in [Section 8.2.3](#)). This includes events occurring during the screening phase of the study, regardless of whether investigational product is administered. Where possible, a diagnosis rather than a list of symptoms should be recorded. If a diagnosis has not been made, then each symptom should be listed individually. All AEs should be captured on the appropriate AE eCRF and in source documents. In addition to AEs, unexpected benefits outside the investigational product indication should also be captured in the source documents and AE eCRF.

All AEs must be followed to closure (ie, the subject’s health has returned to his/her baseline status or all variables have returned to normal), regardless of whether the subject is still participating in the study. Closure indicates that an outcome is reached, stabilization is achieved (the investigator does not expect any further improvement or worsening of the event), or the event is otherwise explained. When appropriate, medical tests and examinations are performed so that resolution of an event(s) can be documented.

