12.3.1.6.3. Severity of Adverse Events

The severity of AEs must be recorded during the course of the event, including the start and stop dates for each change in severity. An event that changes in severity should be captured as a new event. Worsening of pre-treatment events after initiation of the investigational product must be recorded as new AEs. For example, if the subject experiences mild, intermittent headaches prior to dosing with investigational product and the headache intensity increases to moderate after the

first dose of investigational product, a new AE of moderate intermittent headaches is to be recorded in the source documents and eCRF.

The medical assessment of clinical severity of an AE will be determined using the definitions outlined in Common Terminology Criteria for Adverse Events (CTCAE), Version 4.0 (Published May 28, 2009 with Version 4.0.3 on June 14, 2010 by the US Department of Health and Human Services, National Institutes of Health, National Cancer Institute):

Grade 1	Mild; asymptomatic or mild symptoms; or clinical or diagnostic observations only; or intervention not indicated
Grade 2	Moderate; or minimal, local or non-invasive intervention indicated; or limiting age-appropriate instrumental activities of daily living (ADL)
Grade 3	Severe or medically significant but not immediately life-threatening; or hospitalization or prolongation of hospitalization indicated; or disabling; or limiting self-care ADL.
Grade 4	Life-threatening consequences; or urgent intervention indicated.
Grade 5	Death related to AE

It is important to distinguish between severe AEs and SAEs. Severity is a classification of intensity whereas an SAE is an AE that meets serious criteria as described in [Section 12.3.1.6.6.2](#).

Please refer to the above-referenced CTCAE document for full description of CTCAE terms and instrumental and self-care ADLs.

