13.1.2. Statistical Analyses

Analyses of efficacy will focus on the Efficacy Population. Results of endpoints (e.g., CDAI, SES-CD, abdominal pain and loose/watery stool frequency and IBD-Q (CD only; Modified Mayo Score, stool frequency, rectal bleeding, endoscopic appearance, and IBD-Q (UC only) will be summarized by visit for each cohort, both as raw scores and the change from baseline value. For CD, the CDAI individual and total scores will be derived programmatically using recorded data from patient diary, responses to CDAI questions, laboratory tests, and physical exam results.

For UC, the Modified Mayo Score individual and total scores will be derived programmatically using recorded data from patient diary and endoscopy results. Quantitative endoscopy and biopsy results will also be summarized for both the Baseline and End of study visits.

Analyses of safety data will be focused on the Safety Population (as defined in [Section 13.1.1](#)).

Safety variables include treatment-emergent AEs (TEAEs), clinical laboratory results, vital signs measurements, ECG results, and physical examination findings.

Adverse events will be coded using Medical Dictionary for Regulatory Affairs (MedDRA). TEAEs are defined as any AE having first onset or worsening in severity after the first administration of IP. TEAEs will be classified by system organ class (SOC) and preferred term and summarized by the number of subjects reporting each event for each cohort and overall.

For clinical laboratory tests, descriptive summaries of actual (absolute) values and change from baseline values will be presented by cohort for each study visit.

Vital signs (systolic and diastolic blood pressure, pulse, and respiratory rate) and ECG results will be summarized by visit and cohort using appropriate descriptive statistics.

Data in this open-label study will be monitored continually and may be analyzed at any time.

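### Read literally, the TEAE definition in SAP 9.2 counts a pre-dose adverse event that continues after dosing at a lower grade, because each change in severity is a new record with its own start date

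*SAP*

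**What the plan says.** **Recording.** Protocol 12.3.1.6.3 requires severity to be recorded during the event, "including the start and stop dates for each change in severity". It adds: "An event that changes in severity should be captured as a new event". Neither sentence mentions direction. The next sentence takes a specific case: "Worsening of pre-treatment events after initiation of the investigational product must be recorded as new AEs". The worked example there is a headache that gets worse.

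**Collection period.** Protocol 12.3.1.6.2 starts AE collection at consent: "This includes events occurring during the screening phase of the study, regardless of whether investigational product is administered". Under Protocol 12.2, screening can last up to 14 weeks, including any biologic wash-out.

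**Classification.** SAP 9.2 defines a TEAE in two parts joined by *or*. Part 1: it "is an adverse event with onset on or after the first dose administration date". Part 2: it is "an adverse event present before the first dose administration date that worsens (i.e., increases in severity") on or after that date. AEs recorded from consent to first dose "will be considered baseline signs and/or symptoms". All AEs are listed, but only TEAEs are summarised. Repeat TEAEs within a system organ class and preferred term are reduced to the most related or most severe.

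**Protocol definition.** Protocol 13.1.2 words it differently: "TEAEs are defined as any AE having first onset or worsening in severity after the first administration of IP".

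**The concern.** The recording rule and the classification rule work on different units. The protocol splits one clinical event into several records, one per grade. Part 1 of the SAP definition looks only at when a record starts. A fall in grade after dosing therefore produces a record that meets part 1 by its start date, and the worsening test in part 2 is never reached.

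Safety and tolerability is the primary objective, and the TEAE tables are its main summary. A continuing symptom that has eased would appear there as emergent. The study has no control arm against which to see the effect, and with 4 or 6 subjects in a column one subject is a visible share of the table.

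**Working it through.** There is no stated figure to reproduce: the study is descriptive and its sample size rests on feasibility. The check applies the rules to example AE histories and then takes the weight of one subject.

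**Inputs**
- One record per grade, each with its own start date: Protocol 12.3.1.6.3.
- SAP rule: TEAE if the record starts on or after first dose, or if a pre-dose event increases in severity (SAP 9.2).
- Comparison rule: TEAE if the underlying event first starts after first dose, or if its grade rises above the pre-dose grade. This is Protocol 13.1.2 read by underlying event.
- Cohort sizes: 4 Crohn's disease subjects at each of two doses (8 in total) and 6 ulcerative colitis subjects (Protocol 8.7).

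**Step 1: classify example histories**

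| AE history | SAP 9.2, literal, by start date | By underlying event |
|---|---|---|
| Grade 2 before dose, Grade 1 from Day 10 | 1 TEAE record | 0 |
| Grade 3 before dose, then Grade 2, then Grade 1 after dose | 2 TEAE records | 0 |
| Grade 4 before dose, Grade 3 after dose | 1 TEAE record, in the severe row | 0 |
| Grade 1 before dose, Grade 2 after dose | 1 TEAE record | 1 |
| Pre-dose event that resolves outright | 0 | 0 |
| New event after dose | 1 TEAE record | 1 |

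The two readings differ only where a pre-dose event continues at a lower grade. In the second row the subject is counted once for that preferred term, at Grade 2, because repeat TEAEs within a term are collapsed.

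**Step 2: look for a rule that removes the extra record**
- The sentence on baseline signs and symptoms covers AEs recorded before first dose. The lower-grade record starts afterwards.
- The collapsing rule works among TEAEs only. The pre-dose record is not a TEAE, so the lower-grade record can be the subject's only TEAE in that term.
- Neither document links the severity records of one event or excludes decreases in grade.

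**Step 3: weight of one subject**

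Shift in incidence = 1/n.
- Crohn's disease cohort: 1/4 = 25.0 points.
- Crohn's disease total: 1/8 = 12.5 points.
- Ulcerative colitis: 1/6 = 16.7 points.

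For overall TEAE incidence, this needs a subject with no other TEAE. For a preferred term, it needs no other TEAE in that term.

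**Step 4: how often**

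The documents give no rate. If each subject has an assumed probability p of at least one such record, independently, the chance of at least one affected subject among 14 is 1 − (1 − p)^14. For p = 5%, 10%, 20% and 30% this gives 51%, 77%, 96% and 99%. These values illustrate assumed rates only. They also overstate the chance of a change in overall incidence, because they ignore the condition that the subject has no other TEAE.

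**The case against.** The strongest reply is that SAP 9.2 should be read as a whole. Protocol 12.3.1.6.3 also makes a worsening a new AE, so if every new severity record has a fresh onset, part 1 captures all worsenings and part 2 does nothing. Part 2 has a purpose only if it governs continuing pre-dose events, and it asks for an increase in severity. The protocol's specific sentence on pre-treatment events likewise speaks only of worsening, and a site could read the new-record rule for those events that way. This stands as evidence of intent. It does not change the operative wording: the two parts are alternatives, and a program that flags on start date will follow part 1.

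A reader might infer that the SAP has departed from the protocol by dropping the word *first*, and that SAP 14, which declares no changes, conceals this. The documents do not support so firm a reading. A record captured as a new event has its own first onset after dosing, so the protocol wording is open to the same literal result. Read by underlying event, both definitions exclude the improvement. The missing word is not decisive.

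The route to the problem is also narrow. Protocol 8.2.1 has existing conditions reported at the screening visit recorded in the eCRF, and pain, stool frequency and rectal bleeding are diary items. Only a symptom entered as an AE between consent and first dose, and still present at a lower grade after dosing, is affected. The study makes no inference, and all AEs are listed, so a reader of the listing could see both records. These points limit frequency and consequence. They do not correct the tables.

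**Conclusion.** The point holds as a gap between the recording rule and the literal TEAE definition, and it should be closed before database lock. Some improvements in pre-dose AEs would be counted as TEAEs if flagging follows start dates. The error runs one way, because true worsenings and new events are classified alike under either reading.

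The 25-point (n = 4) and 16.7-point (n = 6) shifts in overall incidence are worst cases for one affected subject with no other TEAE. At preferred-term level the same shifts need only that the subject has no other TEAE in that term. The conclusion assumes that sites apply the new-event rule in both directions and that programming uses the start date alone.

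Two further inferences go beyond the documents:
- **That an effective drug would look more toxic.** Nothing shows how many disease symptoms would be entered as pre-dose AEs, so this is speculation.
- **That such records would drift into the related-TEAE table.** SAP 5.7 treats a missing relationship as related, but Protocol 12.3.1.6.4 requires a causality assessment for each AE, so this route is remote.

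**What to change.** In SAP 9.2, state that a TEAE is either an event whose first record starts on or after first dose, or a record of a pre-dose event whose CTCAE grade exceeds the last pre-dose grade of that event. State that records continuing a pre-dose event at the same or a lower grade are listed but not counted.

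Identify continuation records by a variable linking the severity records of one event, or by manual review before database lock. With about 14 subjects, either is a small task.

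With this rule the three improving histories in the table give no TEAEs, and the worsening and the new event still give one each. Restoring the word *first* alone would not be enough, because it leaves open whether a severity record has its own first onset. Changing Protocol 12.3.1.6.3 is optional, since the SAP rule corrects the tables.

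The cost is that TEAE flagging depends on the link between records and no longer on the start date alone. One consequence to accept knowingly: an event that eases after dosing and then returns to its last pre-dose grade, without exceeding it, is not counted.
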